**Table B3. Relevant Medical History**

	Does participant currently have the problem?	Is participant currently receiving treatment?	Does it limit the participant's activities?	
Characteristic	(N= )	(N= )	(N= )	Form Location
Congestive Heart Failure				
Coronary Artery Disease or Myocardial Infarctions.	N (%)	N (%)	N (%)	Relevant Medical History
High Blood Pressure	N (%)	N (%)	N (%)	Relevant Medical History
Lung Disease	N (%)	N (%)	N (%)	Relevant Medical History
Diabetes	N (%)	N (%)	N (%)	Relevant Medical History
Gastrointestinal Disease	N (%)	N (%)	N (%)	Relevant Medical History
Kidney Disease	N (%)	N (%)	N (%)	Relevant Medical History
Liver Disease	N (%)	N (%)	N (%)	Relevant Medical History
Blood Disorder				Relevant Medical History
Cancer (with exception of non-melanoma skin cancer)	N (%)	N (%)	N (%)	Relevant Medical History
Arthritis or Musculoskeletal Disorder (other than Gout)	N (%)	N (%)	N (%)	Relevant Medical History
Thyroid Disease	N (%)	N (%)	N (%)	Relevant Medical History
Chronic Rash				Relevant Medical History

**Table B4. Baseline Labs and Assessment**

Characteristic	Sample (N= )	Form Location
Creatinine (mg/dl)		
Mean ± SD	Mean ± SD	Clinical Bio Lab
Range	Range	Clinical Bio Lab
White Blood Cell (K/CMM)		
Mean ± SD	Mean ± SD	Clinical Bio Lab
Range	Range	Clinical Bio Lab
Platelet Count (K/CMM)		
Mean ± SD	Mean ± SD	Clinical Bio Lab
Range	Range	Clinical Bio Lab
Hemoglobin (Hgb) (g/dl)		
Mean ± SD	Mean ± SD	Clinical Bio Lab
Range	Range	Clinical Bio Lab
C-reactive Protein (CRP) (mg/dl)		
Mean ± SD	Mean ± SD	Clinical Bio Lab
Range	Range	Clinical Bio Lab
Alanine Aminotransferase (ALT) (U/L)		
Mean ± SD	Mean ± SD	Clinical Bio Lab
Range	Range	Clinical Bio Lab
Weight (kg)		
Mean ± SD (N)	Mean ± SD (N)	Vital Signs
Range	(Range)	Vital Signs
Systolic BP		
Mean ± SD (N)	Mean ± SD (N)	Vital Signs
Range	(Range)	Vital Signs
Diastolic BP		
Mean ± SD (N)	Mean ± SD (N)	Vital Signs
Range	(Range)	Vital Signs

**Table B5. Week 24 Labs and Assessment**

Characteristic	Sample (N= )	Form Location
Creatinine (mg/dl)		
Mean ± SD	Mean ± SD	Clinical Bio Lab
Range	Range	Clinical Bio Lab
White Blood Cell (K/CMM)		
Mean ± SD	Mean ± SD	Clinical Bio Lab
Range	Range	Clinical Bio Lab
Platelet Count (K/CMM)		
Mean ± SD	Mean ± SD	Clinical Bio Lab
Range	Range	Clinical Bio Lab
Hemoglobin (Hgb) (g/dl)		
Mean ± SD	Mean ± SD	Clinical Bio Lab
Range	Range	Clinical Bio Lab
C-reactive Protein (CRP) (mg/dl)		
Mean ± SD	Mean ± SD	Clinical Bio Lab
Range	Range	Clinical Bio Lab
Alanine Aminotransferase (ALT) (U/L)		
Mean ± SD	Mean ± SD	Clinical Bio Lab
Range	Range	Clinical Bio Lab
Weight (kg)		
Mean ± SD (N)	Mean ± SD (N)	Vital Signs
Range	(Range)	Vital Signs
Systolic BP		
Mean ± SD (N)	Mean ± SD (N)	Vital Signs
Range	(Range)	Vital Signs
Diastolic BP		
Mean ± SD (N)	Mean ± SD (N)	Vital Signs
Range	(Range)	Vital Signs

**Table B6. Week 48 Labs and Assessment**

Characteristic	Sample (N= )	Form Location
Creatinine (mg/dl)		
Mean ± SD	Mean ± SD	Clinical Bio Lab
Range	Range	Clinical Bio Lab
White Blood Cell (K/CMM)		
Mean ± SD	Mean ± SD	Clinical Bio Lab
Range	Range	Clinical Bio Lab
Platelet Count (K/CMM)		
Mean ± SD	Mean ± SD	Clinical Bio Lab
Range	Range	Clinical Bio Lab
Hemoglobin (Hgb) (g/dl)		
Mean ± SD	Mean ± SD	Clinical Bio Lab
Range	Range	Clinical Bio Lab
C-reactive Protein (CRP) (mg/dl)		
Mean ± SD	Mean ± SD	Clinical Bio Lab
Range	Range	Clinical Bio Lab
Alanine Aminotransferase (ALT) (U/L)		
Mean ± SD	Mean ± SD	Clinical Bio Lab
Range	Range	Clinical Bio Lab
Weight (kg)		
Mean ± SD (N)	Mean ± SD (N)	Vital Signs
Range	(Range)	Vital Signs
Systolic BP		
Mean ± SD (N)	Mean ± SD (N)	Vital Signs
Range	(Range)	Vital Signs
Diastolic BP		
Mean ± SD (N)	Mean ± SD (N)	Vital Signs
Range	(Range)	Vital Signs

**Table B7. Study Medication Adherence**

Adherence	Baseline (n= )	Form Location
Phase 1		
<80%	N (%)	Study Medication Adherence
>= 80%	N (%)	Study Medication Adherence
Phase 2		
<80%	N (%)	Study Medication Adherence
>= 80%	N (%)	Study Medication Adherence
Phase 3		
<80%	N (%)	Study Medication Adherence
>= 80%	N (%)	Study Medication Adherence
Overall		
<80%	N (%)	Study Medication Adherence
>= 80%	N (%)	Study Medication Adherence

Adherence is computed as (Total capsules/Tablets taken/Total capsules/tablets given) \* 100

**Table B8. Study Medication Dose Change**

Adherence	Baseline (n= )	Form Location
Baseline		
< 100/40mg	N (%)	Change in Study Medication dosage
= 100/40mg	N (%)	Change in Study Medication dosage
> 100/40mg	N (%)	Change in Study Medication dosage
3 weeks		
< 200/40mg	N (%)	Change in Study Medication dosage
= 200/40mg	N (%)	Change in Study Medication dosage
> 200/40mg	N (%)	Change in Study Medication dosage
6 weeks		
< 300/40mg	N (%)	Change in Study Medication dosage
= 300/40mg	N (%)	Change in Study Medication dosage
> 300/40mg	N (%)	Change in Study Medication dosage
9 weeks		
< 400/80mg	N (%)	
= 400/80mg	N (%)	
> 400/80mg	N (%)	

**Table B9. Concomitant Medications**

Characteristic	Baseline (n= )	Form Location
Probenecid	N (%)	Concomitant Medications
Lesinurad	N (%)	Concomitant Medications
Angiotensin Converting Enzyme (ACE) Inhibitor	N (%)	Concomitant Medications
Alpha Blocker	N (%)	Concomitant Medications
Angiotensin Receptor Blocker (ARB)	N (%)	Concomitant Medications
Losartan	N (%)	Concomitant Medications

**Table C1. Study Primary Outcome Events**

Outcome Event Type	Sample (N= )	Element Code
Primary Outcome		
# Subjects with more than one gout flare Phase 3	N(%)	Gout flare Questionnaire and diary
Secondary outcome 1		
# Subjects with CKD3 in Phase 3	N(%)	Clinical Biochem Lab
# Subjects with more than one gout flare in Phase 3	N(%)	Gout flare Questionnaire and diary
Secondary outcome 2 and 3		
# Subjects with mean sUA < 6.0 at the end of Phase 2	N(%)	Clinical Biochem Lab
# Subjects with mean sUA < 6.8 at the end of Phase 2	N(%)	Clinical Biochem Lab
Secondary outcome 4		
EQ-5D-3L		
Mean ± SD	Mean ± SD	EQ5D-3L
Range	(range)	EQ5D-3L
VR-12		
Mean ± SD	Mean ± SD	VR-12
Range	(range)	VR-12

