### **3.5. Description of the Efficacy Endpoints**

#### **3.5.1. Primary outcomes**

The primary outcome will be the proportion of participants who have at least one gout flare in the allopurinol group compared with the febuxostat group during Phase 3.

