#### **3.5.2. Secondary outcomes**

The secondary outcomes will include:

- 1) The efficacy and tolerability in patients with CKD 3.
  - i. To determine whether the efficacy of allopurinol and febuxostat differ among those with Stage 3 CKD, a planned secondary endpoint will be the occurrence of gout flares during Phase 3 in this patient subset.

- ii. Tolerability of the two treatments will also be compared in this patient subset and will include comparisons of adverse events, serious adverse events, and related study withdrawal.
- 2) The proportion of patients achieving a sUA < 6.0 mg/dl during Phase 2 (mean level assessed at weeks 36, 42, and 48) across treatment groups.
  - 3) The proportion of having at least one gout flares in Phase 3 differ in those who reach a target sUA of < 6.0 mg/dl compared with those who do not by 48 weeks.
  - 4) The impact of study treatments and sUA levels on health-related quality of life.

Both the five-item EurQol (EQ-5D-3L) and Veterans RAND 12 (VR-12) will be collected from all participants at baseline, 24, 48 and 72 weeks.

- 5) The changes in tophi area by location among those with tophaceous gout across treatment groups and sUA levels.

We anticipate that ~20% of study participants will have tophi at enrollment. The sentinel tophus will be defined as the most prominent and/or most readily measured tophus found at the time of the baseline evaluation on the hands, elbows, feet, or ears (i.e., the most common sites for tophi). Change in tophi area will be examined at week 24, week 48, and week 72 as a secondary outcome among this informative subset of patients with tophaceous gout.

- 6) The impact of treatment on the flare rate over time.

To determine whether the total number of gout flares differs between the two treatment groups the total flare numbers occurring during observation (week 0 to 72) will be compared.

Recognizing that the duration of a gout flare typically extends from several days to 2-3 weeks, and that it may sometimes be difficult for patients to distinguish between two or more back-to-back flares and one persistent but fluctuating flare, a maximum of one gout flare will be counted for each one-month observation period. Thus, as an example, during Phase 3 (24 weeks) patients could experience a number of gout flares ranging from 0 to 6 flares.

- 7) The tolerability/toxicity of the two ULTs.

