### 5.4. Primary Efficacy Analysis

Primary efficacy analysis will include patients who remain on study when phase 3 begins.

The primary outcome is the difference (D) in proportion of patients with one or more gout flares during Phase 3. Seven rheumatologists on our Planning Committee, selected for their expertise in gouty arthritis and clinical trial design, chose  $B = 8\%$ .

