**Section C: Follow-up Assessment**

[figure not shown]
Table C1. Study Primary Outcome Events  
Table C2. Study Secondary Outcome Events – Part I  
Table C2. Study Secondary Outcome Events – Part II  
Table C2. Study Secondary Outcome Events – Part III  
Table C2. Study Secondary Outcome Events – Part IV  
Table C2. Study Secondary Outcome Events – Part V

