**Table C2. Study Secondary Outcome Events – Part I**

Outcome Event Type	Sample (N= )	Element Code
Secondary outcome 1		
# Subjects with CKD3 in Phase 3	N(%)	Clinical Biochem Lab
# Subjects with more than one gout flare in Phase 3	N(%)	Gout flare Questionnaire and diary
Secondary outcome 2 and 3		
# Subjects with mean sUA < 6.0 at the end of Phase 2	N(%)	Clinical Biochem Lab
# Subjects with mean sUA < 6.8 at the end of Phase 2	N(%)	Clinical Biochem Lab

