**Table C5. Study Secondary Outcome Events – Part IV**

Phase	Gout Flare Count	Sample (n= )	Form Location
1	0	N (%)	Gout Attack Diary and Questionnaire
	1-2	N (%)	
	3+	N (%)	
2	0	N (%)	Gout Attack Diary and Questionnaire
	1-2	N (%)	
	3+	N (%)	
3	0	N (%)	Gout Attack Diary and Questionnaire
	1-2	N (%)	
	3+	N (%)	
Overall	0	N (%)	Gout Attack Diary and Questionnaire
	1-2	N (%)	
	3+	N (%)	

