**Table D1. Rates of Non-Serious Adverse Events (NAEs) and Serious Adverse Events (SAEs), by Site**

Site#	# NAEs	#Unique Subjects	Rate per Year*		# SAEs	#Unique Subjects	Rate per Year*
101	N (%)	N (%)			N (%)	N (%)	
102	N (%)	N (%)			N (%)	N (%)	
..	..	..			..	..	
..	..	..			..	..	
125	N (%)	N (%)			N (%)	N (%)	
TOTAL							

\*Rate per year computed as [# events / (sum of (data close date - randomization date))], if events are rare, then present as rate per 100 years.

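### SAP DMC table shells: the flare rows in Tables C1 and C2 count more than one flare where the endpoint is at least one, and Table D1 person-time has no stated stop at the end of participation (minor; DMC reporting only)

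*SAP*

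**What the plan says.** **Flare rows.** SAP 3.5.1 defines the primary outcome as the "proportion of participants who have at least one gout flare in the allopurinol group compared with the febuxostat group during Phase 3". SAP 5.4 agrees: "The primary outcome is the difference (D) in proportion of patients with one or more gout flares during Phase 3". Protocol Section VIII codes the outcome as no flares against one or more. SAP 3.5.2 item 1 takes the occurrence of Phase 3 flares as the endpoint in stage 3 CKD.

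The shells in SAP 7 differ. Under the primary-outcome heading, Table C1 has the row "Subjects with more than one gout flare Phase 3". Under secondary outcome 1 (stage 3 CKD), Tables C1 and C2 both have "Subjects with more than one gout flare in Phase 3". The element-code cell names only the source form. Table C5 gives flare counts by phase as 0, 1-2 and 3+, for the whole sample only.

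**Person-time.** The Table D1 footnote reads "Rate per year computed as [# events / (sum of (data close date - randomization date", and its brackets close there. SAP 3.7 collects AEs from consent to the end of participation and SAEs until 30 days after it. It asks for rates per person-year overall, by arm and by center, and does not define person-time. SAP 6.1 cuts the data for each DMC report four weeks before the meeting and includes participants randomized more than six weeks before it. The term 'data close date' is not defined.

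**The concern.** The label is the only counting rule in each flare row. More than one means two or more, so a programmer who follows the shell drops every participant with exactly one flare. The DMC would then read, under the primary-outcome heading, a smaller event than the trial's endpoint. SAP 4 says that event rates go to the DMC, and SAP 6 has it meet twice a year.

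In Table D1, once participants finish or leave, the formula can keep adding time during which no events are collected. The reported rate then falls with calendar time at a constant true rate, and falls most at sites that enrolled early. The table exists to compare sites.

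**Working it through.** **What the planned 20% refers to.** The documents give no numerical result for Table C1 or D1. The nearest stated figure is the power in Protocol Section VIII: 96%, 91% and 87% at flare rates of 15%, 20% and 25%, with 450 per arm, an 8% margin and one-sided 5%. At 20%, Φ(0.08/√(2 × 0.20 × 0.80/450) − 1.645) = Φ(3.00 − 1.645) = 91.2%. The same formula gives 95.7% and 87.0% at the other two rates, so the stated power reproduces. The 20% is the rate of one or more flares.

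**What a literal flare row would show.** SAP 3.5.2 item 6 states that "a maximum of one gout flare will be counted for each one-month observation period", so Phase 3 has six intervals and a count of 0 to 6. Set P(0) = 0.80.

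- Independent months: p = 1 − 0.80^(1/6) = 0.0365. P(exactly one) = 6 × 0.0365 × (1 − 0.0365)^5 = 0.182. P(two or more) = 0.200 − 0.182 = 0.018.
- Correlated months: beta-binomial with a = m(1 − ρ)/ρ and b = (1 − m)(1 − ρ)/ρ, with m solved so that P(0) = 0.80. The values of ρ are my assumptions; the documents give none.

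| ρ | m | P(two or more) |
|---|---|---|
| 0 | 0.0365 | 1.8% |
| 0.1 | 0.0456 | 5.5% |
| 0.3 | 0.0649 | 9.9% |
| 0.5 | 0.0886 | 12.8% |

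At a true 15% the row shows 1.0% to 9.4%; at 25% it shows 2.9% to 16.3%. For the roughly 317 participants with stage 3 CKD that the protocol plans, and assuming that 20% applies to them, 317 × 0.20 = 63 would have at least one flare. The row would show 317 × 0.018 = 6 to 317 × 0.128 = 41.

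**Table D1 if the data close date is the common DMC cut.** Inputs from SAP 2 are 24 months of recruitment and 72 weeks of follow-up (16.56 months). Inputs from SAP 6.1 are the cut 4 weeks before the meeting (0.92 months) and randomization more than 6 weeks before it (1.38 months). I assume uniform entry, a constant event rate and no dropout, with T the meeting month counted from first entry.

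Let C = T − 0.92, with entry e uniform from 0 to min(24, T − 1.38). The footnote gives each participant C − e; time under AE observation is min(16.56, C − e). Reported rate ÷ true rate = mean of min(16.56, C − e) ÷ mean of (C − e).

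At T = 30, C = 29.08, so C − e runs from 5.08 to 29.08 with mean 17.08. The capped mean is [(16.56² − 5.08²)/2 + 16.56 × (29.08 − 16.56)]/24 = (124.2 + 207.3)/24 = 13.81. The ratio is 13.81/17.08 = 0.81. For SAEs the cap is 16.56 + 0.99 = 17.55 months.

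| Meeting month | AE rate ÷ true | SAE rate ÷ true |
|---|---|---|
| 12 | 1.00 | 1.00 |
| 18 | 0.999 | 1.00 |
| 24 | 0.920 | 0.942 |
| 30 | 0.809 | 0.838 |
| 36 | 0.690 | 0.722 |

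By site at T = 30: one that enrolled only in months 0-12 has mean C − e of 23.08 and every participant past 16.56, so 16.56/23.08 = 0.72. One that enrolled only in months 12-24 gives 0.999.

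**If it is each participant's own last date**, C − e is already the observed time and the ratio is 1 throughout.

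**The case against.** *The flare label is a wording slip that nobody would program.* The endpoint is explicit and consistent in both documents, the row sits under the primary-outcome heading, and the shells are marked as subject to change. For the full cohort, subtracting the zero-flare count in Table C5 recovers the right number. This stands as a reason to rate the point minor. It does not correct the row, and C5 has no CKD rows. SAP 6.2 also lists "Table C2. Study Secondary Outcome Events – Part III", whose shell is not visible, so I make no claim about its content.

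*The D1 problem is an undefined term, not a proven error.* That is fair: every D1 percentage depends on the common-cut reading. It is the natural one, since SAP 6.1 describes a single calendar cut per report, but SAP 6.1 does not use the term. The site contrast is also an extreme pattern, and Table D1 prints event and subject counts beside each rate.

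A reader might infer three stronger things that the documents do not support:

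- That the final test would use two or more flares. SAP 5.4 uses one or more, and no interim analysis is planned.
- That conditional power would be computed from the Table C1 row. Protocol Section XX says the DMC receives conditional power estimates; nothing ties them to this shell.
- That final-report AE rates will be understated. The footnote belongs to one by-site DMC shell, and nothing extends it to the rates in SAP 3.7.

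**Conclusion.** Three flare rows are wrong as written against the SAP's own endpoint. Followed literally, they show less than the planned 20%. That direction is certain; the 2% to 13% range rests on assumed correlations.

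The Table D1 formula lacks a stop that the AE and SAE collection windows call for. Under a common cut with the SAP 6.1 windows, uniform accrual and no dropout, by-site AE rates are essentially right to month 18 and then drift to about 92% of true at month 24 and 81% at month 30, with earlier-enrolling sites diluted more.

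Severity is minor and confined to DMC reporting. The final primary analysis, sample size, power and event counts do not change. With 1:1 randomization and similar dropout, both arms' person-time is inflated alike, so between-arm rate ratios barely move.

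**What to change.** 1. Relabel the three rows (primary outcome in Table C1; secondary outcome 1 in Tables C1 and C2) *Subjects with at least one gout flare in Phase 3*.
2. In the Table D1 footnote, define the data close date. End each participant's time at the earliest of data close, death and end of participation for AEs, and of data close, death and end of participation plus 30 days for SAEs. Express it in years (days ÷ 365.25, as Table B1 does for age), and count events over the same window as the time.
3. Use the same person-time for any rate reported under SAP 3.7, which currently defines none.

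The cost is three labels, one footnote and the programs behind them. Each participant's end date is needed. Table A6 takes termination reasons, including death, from the End of Study form but shows no dates, so confirm that the form records them.

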**Table C2. Study Secondary Outcome Events – Part I**

Outcome Event Type	Sample (N= )	Element Code
Secondary outcome 1		
# Subjects with CKD3 in Phase 3	N(%)	Clinical Biochem Lab
# Subjects with more than one gout flare in Phase 3	N(%)	Gout flare Questionnaire and diary
Secondary outcome 2 and 3		
# Subjects with mean sUA < 6.0 at the end of Phase 2	N(%)	Clinical Biochem Lab
# Subjects with mean sUA < 6.8 at the end of Phase 2	N(%)	Clinical Biochem Lab

**Table C3. Study Secondary Outcome Events – Part II**

Outcome Event Type	Sample (N= )	Element Code
Secondary outcome 4		
EQ-5D-3L Baseline		
Mean ± SD	Mean ± SD	EQ5D-3L
Range	(range)	EQ5D-3L
VR-12 Baseline		
Mean ± SD	Mean ± SD	VR-12
Range	(range)	VR-12
EQ-5D-3L Week 24		
Mean ± SD	Mean ± SD	EQ5D-3L
Range	(range)	EQ5D-3L
VR-12 Week 24		
Mean ± SD	Mean ± SD	VR-12
Range	(range)	VR-12
EQ-5D-3L Week 48		
Mean ± SD	Mean ± SD	EQ5D-3L
Range	(range)	EQ5D-3L
VR-12 Week 48		
Mean ± SD	Mean ± SD	VR-12
Range	(range)	VR-12

**Table C5. Study Secondary Outcome Events – Part IV**

Phase	Gout Flare Count	Sample (n= )	Form Location
1	0	N (%)	Gout Attack Diary and Questionnaire
	1-2	N (%)	
	3+	N (%)	
2	0	N (%)	Gout Attack Diary and Questionnaire
	1-2	N (%)	
	3+	N (%)	
3	0	N (%)	Gout Attack Diary and Questionnaire
	1-2	N (%)	
	3+	N (%)	
Overall	0	N (%)	Gout Attack Diary and Questionnaire
	1-2	N (%)	
	3+	N (%)	

**Table C6. Study Secondary Outcome Events – Part V**

Phase	Toxicity Events	Sample (n=)	Form Location
Rise in sUA levels			
1	Mean ± SD	N (%)	Clinical Biochem Lab
2	Mean ± SD	N (%)	Clinical Biochem Lab
3	Mean ± SD	N (%)	Clinical Biochem Lab
Overall	Mean ± SD	N (%)	Clinical Biochem Lab
Skin Rashes			
1	0	N (%)	Rash Adverse Event
	1-2	N (%)	
	3+	N (%)	
2	0	N (%)	Rash Adverse Event
	1-2	N (%)	
	3+	N (%)	
3	0	N (%)	Rash Adverse Event
	1-2	N (%)	
	3+	N (%)	
Overall	0	N (%)	Rash Adverse Event
	1-2	N (%)	
	3+	N (%)	

**Table D1. Rates of Non-Serious Adverse Events (NAEs) and Serious Adverse Events (SAEs), by Site**

Site#	# NAEs	#Unique Subjects	Rate per Year*		# SAEs	#Unique Subjects	Rate per Year*
101	N (%)	N (%)			N (%)	N (%)	
102	N (%)	N (%)			N (%)	N (%)	
..	..	..			..	..	
..	..	..			..	..	
125	N (%)	N (%)			N (%)	N (%)	
TOTAL							

\*Rate per year computed as [# events / (sum of (data close date - randomization date))], if events are rare, then present as rate per 100 years.

**Table D2. Summary of Non-Serious Adverse Events**

	Sample (N= Events)	Form Location	Element Codes
#Weeks since Randomization	Mean±SD	Randomization and AE	
Phase 1	N(%)	Randomization and AE	
Phase 2	N(%)	Randomization and AE	
Phase 3	N(%)	Randomization and AE	
Severity of NAE			
Mild AEs	N(%)	AE	AESEV=1
Moderate AEs	N(%)	AE	AESEV =2
Severe AEs	N(%)	AE	AESEV=3
Relatedness			
Possibly or Definitely Related to Study Treatment	N(%)	AE	AEIVREL=yes, possibly
# Unique Subjects with at least 1 NAE that is possibly or definitely related to Study Treatment	N*(%) of N subjects	AE	)

**Table D3. Summary of Serious Adverse Events**

Characteristic	Sample (N= Events)	Form Location	Element Codes
#Weeks since Randomization	Mean+SD	Randomization and SAE	
Phase 1	N(%)	Randomization and SAE	
Phase 2	N(%)	Randomization and SAE	
Phase 3	N(%)	Randomization and SAE	
SAE category (can be multiple)			
Death	N(%)	SAE	AESDTH=1
Initial or prolonged hospitalization	N(%)	SAE	AESHOSP=1
Life threatening experience	N(%)	SAE	AESLIFE=1
Required medical or surgical treatment	N(%)	SAE	AESMIE=1
Persistent or significant disability or incapacity	N(%)	SAE	AESDISAB=1
Congenital anomaly/birth defect	N(%)	SAE	AESCONG=1
Relatedness (Possibly or Definitely)			
To Study Treatment	N(%)	SAE	
# Unique Subjects with at least 1 SAE that is possibly or definitely related to Study Treatment	N*(%) of N subjects	SAE	
# Unique Subjects with at least 1 SAE that is possibly or definitely related to Study Drug Capsule	N*(%) of N subjects	SAE	
Outcome			
Recovered/resolved	N(%)	SAE	AESOUT =1
Recovered/resolved with sequelae	N(%)	SAE	AESOUT =2
Recovering/resolving	N(%)	SAE	AESOUT =3
Not recovered/not resolved	N(%)	SAE	AESOUT =3
Fatal 5	N(%)	SAE	AESOUT =5
Data not available	N(%)	SAE	AESOUT =6

